10.2. Permanent Discontinuation of Study Drug

Any subject who is permanently discontinued from investigational product for an AE or abnormal laboratory result should have the reason for investigational product discontinuation reported as the AE or abnormal laboratory value.

Patients will discontinue study drug if the following disease related clinical events occur during the study period:

- Unprovoked venous thromboembolism (deep vein thrombosis, pulmonary embolism)
- GCA relapse occurs with objective evidence of severe ischemic event (vision loss, stroke, critical limb ischemia)
- Second GCA relapse occurs during study period

Patients will discontinue study drug following temporary interruption of the study drug if either of the following occurs.

- Study drug has been held due to a study drug-related laboratory abnormality necessitating temporary interruption (Table 3) and the laboratory abnormality that led to the investigational hold has not returned to a level at which the investigational product can be resumed (Table 3) by 4 weeks (28 days) for renal function (as determined by eGFR) or 6 weeks for the remaining laboratory parameters (42 days) from the date investigational hold commenced. For example: Example 1: a patient would be withdrawn from the study if the renal function declined due to study drug (i.e. not intercurrent illness) and the eGFR decreased to 30 mL/min/1.73m² and hold

commenced on January 1st.but the eGFR had not returned to ≥ 50 mL/min/1.73 m² by January 29th. Example 2: a patient would be withdrawn from the study if the WBC count decreased below <2000 cells/ μ L on January 1st and did not return to a value of >2500 cells/ μ L by February 11th.

- If following a study drug interruption for an identified laboratory abnormality (Table 3) the same laboratory parameter that led to study drug interruption is again affected by reinitiation of study drug. For example, platelet count prior to study drug was 150,000/uL but decreases to 50,000/uL while on the study drug. Study drug is held and the platelet count improves to 125,000/uL allowing reinitiation of study drug. Following reinitiation the platelet count decrease again to 50,000/uL.
-

In addition discontinuation of the study drug will occur if any one of the following laboratory abnormalities occur:

- ALT or AST >8 x ULN
- ALT or AST >5 x ULN for more than 2 weeks after temporary interruption of investigational product
- ALT or AST >3 x ULN and either total bilirubin level (TBL) >2 x ULN or INR >1.5 x ULN
- ALT or AST >3 x ULN with the appearance of fatigue, nausea, vomiting, right upper-quadrant pain or tenderness, fever, rash, and/or eosinophilia ($>5\%$)
- Alkaline phosphatase (ALP) >3 x ULN
- ALP >2.5 x ULN and TBL >2 x ULN
- ALP >2.5 x ULN with the appearance of fatigue, nausea, vomiting, right upper quadrant pain or tenderness, fever, rash, and/or eosinophilia ($>5\%$).

Subjects should be discontinued from the investigational product in the following circumstances:

- WBC count <1000 cells/ μ L
- ANC <500 cells/ μ L
- Lymphocyte count <200 cells/ μ L
- Hemoglobin <6.5 g/dL

For lab values that meet permanent discontinuation thresholds, the study drug will be discontinued unless, in the opinion of the investigator, the lab abnormality is due to intercurrent illness or another identified factor. Lab tests may be repeated within 1 week to confirm whether discontinuation criteria have been met. Furthermore, if investigational product is not discontinued due to intercurrent illness, the investigator must confirm the lab value no longer meets discontinuation thresholds following the resolution of the intercurrent illness or other identified factor.

In addition, subjects will be discontinued from investigational product in the following circumstances:

- Pregnancy
- Malignancy (except for successfully treated basal cell or squamous epithelial skin cancers)

Some possible reasons that may lead to permanent discontinuation include:

- Enrollment in any other clinical trial involving an investigational product or enrollment in any other type of medical research judged not to be scientifically or medically compatible with this study
- Participation in the study needs to be stopped for medical, safety, regulatory, or other reasons consistent with applicable laws, regulations, and good clinical practice (GCP)
- Investigator Decision
 - the investigator decides that the patient should be discontinued from the study
- Subject Decision
 - the subject requests to be withdrawn from the study.

The following actions must be taken in relation to a subject that fails to attend the clinic for a required study visit.

- Site must attempt to contact the subject and re-schedule the missed visit as soon as possible
- The site must counsel the subject on the importance of maintaining the assigned visit schedule and ascertain whether or not the subject wishes to and/or should continue in the study
- In cases deemed “lost to follow-up”, the investigator must make every effort to regain contact with the subject (up to 3 phone calls to listed number and if necessary a certified letter to last known mailing address or local equivalent methods). These contact attempts will be documented in the medical record.
- Should the subject be unreachable, only then will the subject be considered to have withdrawn from the study with a primary reason of “lost to follow-up”.

Subjects who have withdrawn prematurely from the study should attend an early withdrawal visit and undergo the 12 week post-study drug follow-up period for evaluation of safety.

Subjects withdrawn prematurely from the study can be replaced by a new study entry if the study is still openly enrolling (that is has not reached enrollment of 15 subjects).

11. STUDY ENDPOINTS

Primary endpoint:	
The primary endpoint is safety.
 
The measure by which this will be determined is the following:
 
 • Incidence of adverse events (AEs) and serious adverse events (SAEs) related to the study drug
Secondary endpoint	
The secondary endpoint preliminary efficacy of baricitinib (4mg, oral, daily) in patients with relapsing GCA.
 
The measures by which this will determined are the following:

	
 • Relapse-free survival at week 52 • Relapse-free survival at week 24 • Duration of glucocorticoid-free remission • Number of relapses per subject over time • Change from baseline erythrocyte sedimentation rate (ESR) to end of study • Change from baseline C-reactive protein to end of study • Glucocorticoid dose (mg) at week 52 compared to enrollment • Change in BVAS from baseline to end of study
--	---

12. STUDY MONITORING AND ADVERSE EVENT REPORTING

12.1 Study Monitoring, Auditing and Inspecting

12.1.1 Study Monitoring Plan

As a service to the sponsor-investigator and to assist with the sponsor regulatory obligation to monitor study progress, this study will be periodically monitored during the conduct of the trial by staff from the Mayo Clinic Office of Research Regulatory Support (ORRS). Clinical trial monitoring may include but will not necessarily be limited to review of the study regulatory documents, source data and database entries throughout the duration of the study to help ensure the validity and integrity of the data. Original informed consent forms will be reviewed. Written monitoring reports with findings and recommended and suggested corrective actions will be provided to the sponsor.

12.1.2 Auditing and Inspecting

The investigator will permit study-related monitoring by ORRS and audits by the IRB Compliance Unit, if indicated, as well as inspections by authorized representative of government regulatory agencies such as FDA of all study related documents (e.g. source documents, regulatory documents, data collection instruments, drug accountability records and study data etc.). The investigator will ensure access is granted for inspection of applicable study-related facilities (e.g. pharmacy, diagnostic laboratories, etc.).

Participation as an investigator in this study implies acceptance of potential inspection by government regulatory authorities and applicable compliance offices.

12.1.3 Ethical Considerations

This study is to be conducted according to applicable United States government regulations and Institutional research policies and procedures.

This protocol and any amendments as well as subject materials such as the informed consent/assent forms will be submitted to a properly constituted Mayo Clinic Institutional Review Board (IRB) for review and formal approval. The decision(s) of the IRB concerning the conduct of the study will be made in writing to the sponsor-investigator before commencement of this study.

All subjects for this study will be provided a consent (or assent) form describing this study and providing sufficient information for subjects to make an informed decision about their participation in this study. The

formal consent of a subject, using the IRB approved consent or assent form, must be obtained before subject undergoes any study procedure. The consent form must be signed and dated by the subject or the subject's legally authorized representative, as well as the individual obtaining the informed consent

12.2. Safety

The Study Principal Investigator has primary oversight responsibility for the clinical trial. All co-investigators will report AEs and SAEs to the principal investigator upon alert of occurrence. Safety will be assessed from the documentation of adverse events and review of vital signs and laboratory assessments including complete blood counts, serum chemistry profiles, fasting serum lipids, and hepatitis B and C serologies. Adverse events (including serious and opportunistic infections, cardiovascular events, gastrointestinal perforations, hepatic laboratory abnormalities, and cytopenia) will be monitored on a regular and/or event-driven basis throughout the study.

The definitions of an adverse event (AE) or serious adverse event (SAE) in the following section will comply with the International Council for Harmonisation of Technical Requirements for Pharmaceuticals for Human Use (ICH) guidelines for good clinical practice and applies the standards set forth in the National Cancer Institute (NCI) Common Terminology Criteria for Adverse Events version 4.0.

12.3. Adverse Events

An adverse event (AE) will be defined as any unfavorable and unintended sign (including abnormal laboratory finding), symptom, or disease temporally associated with the use of a medical treatment or procedure that may or may not be considered related to the medical treatment or procedure.

Events meeting AE definition include:

Any abnormal laboratory test results (hematology, clinical chemistry, or urinalysis) or other safety assessments (e.g., ECGs, radiological scans, vital signs measurements), including those that worsen from baseline, and felt to be clinically significant in the medical and scientific judgment of the investigator.

- Exacerbation of a chronic or intermittent pre-existing condition including either an increase in frequency and/or intensity of the condition.
- Signs, symptoms, or the clinical sequelae of a suspected interaction.
- Signs, symptoms, or the clinical sequelae of a suspected overdose of either study treatment or a concomitant medication (overdose per se will not be reported as an AE/SAE unless this is an intentional overdose taken with possible suicidal/self-harming intent. This should be reported regardless of sequelae).
- "Lack of efficacy" or "failure of expected pharmacological action" per se will not be reported as an AE or SAE. However, the signs and symptoms and/or clinical sequelae resulting from lack of efficacy will be reported if they fulfil the definition of an AE or SAE.

Events that do not meet AE definition include:

Any clinically significant abnormal laboratory findings or other abnormal safety assessments which are associated with the underlying disease, unless judged by the investigator to be more severe than expected for the subject's condition.

- The disease/disorder being studied or expected progression, signs, or symptoms of the disease/disorder being studied, unless more severe than expected for the subject's condition.
- Medical or surgical procedure (e.g., endoscopy, appendectomy): the condition that leads to the procedure is an AE.
- Situations where an untoward medical occurrence did not occur (social and/or convenience admission to a hospital).

- Anticipated day-to-day fluctuations of pre-existing disease(s) or condition(s) present or detected at the start of the study that do not worsen.

12.4. Serious Adverse Event

Defined according to 21CFR 312.32. A serious adverse event (SAE) is any untoward medical occurrence that at any dose

- Results in death
- Is life-threatening
- Requires hospitalization or prolongs existing hospitalization
- Is a congenital anomaly/birth defect
- An important medical event may be considered an SAE when, based upon appropriate medical judgment, it may jeopardize the subject and may require medical or surgical intervention to prevent one of the outcomes listed above

12.5. Toxicity Grading of Adverse Events

Toxicity grades for AE will be assessed using the National Cancer Institute (NCI) Common Terminology Criteria for Adverse Events (CTCAE). AEs will be recorded and graded 1 to 5 according to the CTCAE grade outlined below:

- Grade 1 = mild adverse event
- Grade 2 = moderate adverse event
- Grade 3 = severe and undesirable adverse event
- Grade 4 = life-threatening or disabling adverse event
- Grade 5 = death

12.6. Time Period and Frequency for Collecting Event Information

- AEs and SAEs will be collected from the start of Study Treatment until the 12 week follow-up visit and documented at time of occurrence and each study visit.
- Medical occurrences that begin prior to the start of study treatment but after obtaining informed consent may be recorded on the Medical History/Current Medical Conditions section and will not be considered treatment related side effects.
- Any SAEs assessed as related to study participation or related to the investigational product will be recorded from the time a subject consents to participate in the study up to and including any follow-up contact.
- All SAEs will be recorded and reported to the Sponsor (Mayo Clinic) and Eli Lilly [Investigational Product (IP) Manufacturer] within 24 hours.
- Investigators are not obligated to actively seek AEs or SAEs in former study subjects (those whom have completed the study including the 12 weeks post-study drug visit). However, if the investigator learns of any SAE, including a death, at any time after a subject has been discharged from the study, and he/she considers the event reasonably related to the study treatment or study participation, the investigator must promptly notify Mayo Clinic (Sponsor) and the IP manufacturer.

12.7 Method of Detecting AEs and SAEs

Open-ended and non-leading verbal questioning of the subject will be used to inquire about AE occurrence. Such questions include:

- “How are you feeling?”

- “Have you had any (other) medical problems since your last visit/contact?”
- “Have you taken any new medicines, other than those provided in this study, since your last visit/contact?”

12.8. Follow-up of AEs and SAEs

After the initial AE/SAE report, the investigator is required to proactively follow each subject at subsequent visits/contacts. All SAEs, and non-serious AEs of special interest will be followed until resolution, until the condition stabilizes, until the event is otherwise explained, or until the subject is lost to follow-up. All SAEs and their outcomes will be reported to the Food and Drug Administration (FDA).

AEs of special interest include total or partial blindness, limb claudication, and scalp or tongue necrosis. In addition, severe disease flares, including hospitalizations will be monitored.

Other AEs of special interest for baricitinib are hematologic laboratory abnormalities, hepatobiliary laboratory abnormalities and lipid parameter abnormalities. Changes in these values leading to temporary or permanent discontinuation of the study drug will be reported as an AE. Additional events of interest include serious CV events, infections and malignancies.

All initial reports of cardiovascular AEs (myocardial infarction, stroke, death, hospitalization for angina, hospitalization for TIA), newly identified malignancies and active TB will be recorded by the investigational staff within 24 hours of their knowledge of the event even if these events do not meet the definition of a SAE.

Glucocorticoid-related AEs such as diabetes mellitus, osteoporosis, fractures, infection, glaucoma, and cataracts among others will be evaluated in relation to steroid exposure and baseline risk.

12.9. Cardiovascular and Death Events

All cardiovascular events and all deaths, whether or not they are considered SAEs, will be documented. Major Adverse Cardiovascular Events (MACE), defined as myocardial infarction, stroke, death, hospitalization for unstable angina, and hospitalization for TIA, will be collected.

Definition of Cardiovascular Events:

Investigators will be required to fill out an adverse event form for the following cardiovascular events if they occur in the subject following the initiation of study drug.

- Myocardial infarction/unstable angina
- Congestive heart failure
- Arrhythmias
- Valvulopathy
- Pulmonary hypertension
- Cerebrovascular events/stroke and transient ischemic attack
- Peripheral arterial thromboembolism
- Deep vein thrombosis/pulmonary embolism
- Revascularization

12.10. Regulatory Reporting Requirements for SAEs

Prompt notification by the investigator to the Sponsor and the FDA of all SAEs related to study treatment is essential so that legal obligations and ethical responsibilities towards the safety of subjects and the safety of a product under clinical investigation are met. Upon identification or knowledge of a SAE, investigators will alert the Sponsor and the IP manufacturer within 24-hours through MedWatch reporting form.

The Sponsor has a legal responsibility to notify both the local regulatory authority and other regulatory agencies about the safety of a product under clinical investigation. The Sponsor will comply with regulatory requirements relating to safety reporting to the regulatory authority, Institutional Review Board (IRB)/Independent Ethics Committee (IEC) and investigators.

Investigator safety reports are prepared for suspected unexpected serious adverse reactions according to local regulatory requirements and Eli Lilly policy and are forwarded to investigators as necessary.

An investigator who receives an investigator safety report describing a SAE(s) or other specific safety information (e.g., summary or listing of SAEs) from the IP manufacturer will notify the IRB/IEC, if appropriate according to local requirements.

Expedited Adverse Event Reporting Criteria to the IP Manufacturer (Eli Lilly)

The PI or designee will report all Serious Adverse Events to the IP Manufacturer within 24 hours of the Investigator(s) becoming aware of them.

Fax all SAE forms to: Lilly Global Patient Safety at [contact]

Additionally, the IP manufacturer will be provided with copies of all investigational product-related reports submitted to regulatory authorities.

12.11. Pregnancy

Given the age group under investigation, pregnancy during the course of the study is unlikely. Nevertheless, if a pregnancy is reported then the investigator will inform the IP manufacturer, Eli Lilly, within 24 hours of learning of the pregnancy.

Female subjects who become pregnant during the study must have study drug withdrawn immediately and be withdrawn from the study. An early withdrawal visit and 12-week follow-up will still occur. Information regarding the patient and fetal outcome for patients that become pregnant during the study will continue until the end of the pregnancy and result of the final outcome will be reported to the IP manufacturer for monitoring purposes.

12.12. Physical Exams

A complete physical examination will be conducted during screening and will include, at a minimum, assessment of the Cardiovascular, Respiratory, Gastrointestinal, Vascular and Neurological systems. Height and weight will also be measured and recorded.

A brief physical examination will be conducted at all other time points and include, at a minimum assessments of the skin, lungs, CV system, and abdomen (liver and spleen). Investigators will pay special attention to clinical signs related to previous serious illnesses.

12.13. Vital Signs

Vital signs will be measured in seated position and will include temperature, systolic and diastolic blood pressure and pulse rate.

12.14. Clinical Safety Laboratory Assessments

All laboratory tests with values that are considered clinically significantly abnormal during participation in the study or within 12 weeks after the last dose of study treatment will be repeated until the values return to normal or baseline.

13. SAMPLE SIZE AND COMPUTATION RATIONALE

The study is intended to examine safety and to explore preliminary signal of efficacy. The sample size of 15 was based upon a sufficient number of subjects to begin such explorations prior to pursuit of a

randomized controlled trial. With an accrual of 15 evaluable subjects, there is a 95% confidence that any AE (or SAE) with an incidence of at least 18% will be reported. The standard error of the estimate of the incidence of reported AEs will not exceed 13%.

A historical cohort of patients with biopsy-proven GCA from the Mayo Clinic has recently been reported [16]. In this large single-institution cohort, we found the rate of second relapse in the subset of patients with at least one relapse was 50% at one year (or 50% relapse-free survival at one year). These relapses occurred during GC treatment performed at the discretion of the treating provider and patients were not subject to an accelerated taper, thus likely overestimating relapse-free survival at one year after initial relapse. A recent completed clinical trial evaluating the use of abatacept in GCA with standardized taper has been completed and preliminary results are available [42]. Relapse-free survival at one year in the placebo group was 31% and 48% in the treatment group. The relapse-free survival in Langford et al. study may also be slightly overestimated because all patients received three months of study drug prior to undergoing a standardized GC taper. Prior clinical trials in GCA have observed one year relapse-free survival among placebo groups to range from 10-29% [23,24,43]. With a sample size of 15 patients, an exact binomial test will have 80% power to detect an additional 37% above the expected relapse-free rate with a 0.05 one sided-significance level. Based on available clinical trial data and the preliminary results from Langford et al. [42] a conservative expected relapse-free survival in patients with relapsing GCA receiving only GC and undergoing an accelerated taper would be a 30% relapse-free survival at one year. As such, evidence of efficacy can be identified if 10 of 15 (67%) patients receiving study drug remain relapse-free during the study period.

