5.5. Design Justification

This is a single-center, open-label study to evaluate the safety of baricitinib in GCA and to develop preliminary evidence of efficacy to support the potential conduct of a larger randomized trial.

The design of this study is similar in to other open-label phase II studies evaluating biologic medications in subjects with GCA [29, 38].

Glucocorticoids represent the only current standard of care treatment for patients with GCA. As such, prednisone will be continued during the initiation of the study drug. Subjects will enter the study at one of three doses of prednisone (30 mg, 20 mg, or 10 mg). Subjects should be on a stable prednisone dose for a minimum of 2 weeks (maximum 6 weeks) prior to initiation of study drug. Following study drug initiation prednisone tapering will occur in a standardized manner.

The 52-week study duration was chosen to assess for safety of medication use as well as to observe preliminary evidence of efficacy based on duration of glucocorticoid-free remission and relapse-free survival.

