14. STATISTICAL ANALYSIS PLAN

The primary purpose of this pilot study is to evaluate the safety of baricitinib in subjects with GCA. No specific statistical hypothesis tests are planned. Safety data will be summarized for all treated subjects using appropriate tabulations, descriptive statistics, and graphical presentations. The incidence rate of each AE will be estimated and reported as number (n) and percentage (%).

Descriptive statistics will be provided for all secondary outcome measures. Differences between glucocorticoid dose (mg), C-reactive protein (mg/L), erythrocyte sedimentation rate (mm/hr) and BVAS score from baseline to end of study will be calculated and reported with means and standard deviations. The proportion of subjects in sustained remission will be reported with exact 95% confidence intervals. Kaplan-Meier methods will be used to evaluate relapse-free survival and the duration of glucocorticoid-free remission. Number of relapses per subject over time will be reported as relapses/year.

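### Section 13 offers 10 of 15 (67%) as the result that identifies efficacy, but 67% is the assumed alternative rate; the test with the stated 80% power rejects at 9 of 15

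*Combined protocol and SAP*

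**What the plan says.** Three statements in Section 13 (Sample Size and Computation Rationale) belong together.

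- The test and its power: "an exact binomial test will have 80% power to detect an additional 37% above the expected relapse-free rate with a 0.05 one sided-significance level", with a sample size of 15.
- The expected rate on glucocorticoids alone: patients "undergoing an accelerated taper would be a 30% relapse-free survival at one year". It is supported by an abatacept trial in which "Relapse-free survival at one year in the placebo group was 31% and 48% in the treatment group", and by placebo rates of 10% to 29% in earlier trials. A historical cohort rate of 50% is also cited and described as a likely overestimate.
- The conclusion drawn from these: "evidence of efficacy can be identified if 10 of 15 (67%) patients receiving study drug remain relapse-free during the study period".

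Section 5.5 gives the purpose that such a benchmark serves, namely to "develop preliminary evidence of efficacy to support the potential conduct of a larger randomized trial". Section 14 plans no hypothesis tests. For this endpoint it says that "Kaplan-Meier methods will be used to evaluate relapse-free survival and the duration of glucocorticoid-free remission".

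**The concern.** The last sentence of Section 13 is presented as following from the test just described, so a reader will take 10 of 15 as the smallest number of relapse-free patients that counts as evidence of efficacy. But the percentage attached to it is the expected rate plus the detectable difference. An alternative rate and a rejection boundary are different things. A test with 80% power at a given rate must reject on some results below that rate, because the observed proportion falls below the true one in a large share of trials.

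This is the only efficacy benchmark in the document. If the trial ended with 9 of 15 relapse-free, the test that Section 13 describes would reject 30%, while the sentence would suggest that the result fell short. That could weigh wrongly on the case for a larger randomised trial. The error cannot work the other way: 10 of 15 does reject 30%, so the sentence cannot produce a false claim of efficacy.

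**Working it through.** **Inputs, all from Section 13.** n = 15; exact one-sample binomial test; one-sided alpha 0.05; null rate p0 = 0.30; alternative p1 = 0.30 + 0.37 = 0.67; stated power 80%.

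**Formulas.** For a cut-off r, the attained alpha is P(X ≥ r | n = 15, p = 0.30) and the power is P(X ≥ r | n = 15, p = 0.67). The boundary of the test is the smallest r whose attained alpha is at most 0.05.

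**Results.**

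| Reject at | Attained alpha (p = 0.30) | Power (p = 0.67) | One-sided 95% lower bound for exactly r of 15 |
|---|---|---|---|
| r = 8 | 0.05001 (just over 0.05) | 91.6% | 30.0% (0.29999) |
| r = 9 | 0.01524 | 80.5% | 36.0% |
| r = 10 | 0.00365 | 62.9% | 42.3% |

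**Reproducing the plan's figure.** The smallest r with alpha at or below 0.05 is 9, and its power at 67% is 80.5%. That matches the stated 80%. Taking p1 as exactly 10/15 gives 79.7%. A normal approximation gives 92.6%, or 87.9% with a continuity correction, so the stated 80% agrees with the exact test at a boundary of 9 and not with an approximation.

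**Reading 10 of 15 as the minimum.** Power at 67% is 62.9% (61.8% at 10/15). The loss is 80.5 − 62.9 = 17.6 points. This equals the probability of exactly 9 relapse-free patients: P(X = 9 | 0.67) = 5005 × 0.67^9 × 0.33^6 = 0.176. Solving P(X ≥ r | p) = 0.80 for the true rate gives p = 0.668 for r = 9 and p = 0.728 for r = 10. With a cut-off of 10, the difference detectable with 80% power is therefore 72.8 − 30 = about 43 points, not 37.

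**What 9 of 15 would show.** Observed 60%; one-sided p = 0.015; exact two-sided 95% interval 32.3% to 83.7%, which excludes 30%.

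**Sensitivity to the benchmark.** One-sided error if the true control rate differs from 30%:

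| Control rate | Cut-off 9 | Cut-off 10 |
|---|---|---|
| 29% (top of the earlier placebo range) | 1.2% | 0.3% |
| 31% (abatacept trial placebo group) | 1.9% | 0.5% |
| 50% (historical cohort) | 30.4% | 15.1% |

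A cut-off of 9 holds the error at or below 5% for control rates up to just under 36%; a cut-off of 10 does so up to about 42%. At p0 = 0.29 the boundary moves down to 8 (attained alpha 0.041). At 0.31 and 0.35 it stays at 9.

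**The case against.** The strongest reply is that the sentence is true as written. It does not say at least or only if; 10 of 15 does reject 30% (p = 0.0037); and the paragraph may simply be expressing the detectable difference as a number of patients. The reply continues that Section 14 plans no test, that efficacy is secondary, that no passage ties 10 of 15 to a decision to proceed, and that the Kaplan-Meier estimate will be reported whatever Section 13 says. Finally, a boundary of 9 is fragile, since 8 misses by 0.00001 and becomes the boundary at 29%. Writing it in would lower the bar in an open-label, single-arm trial whose benchmark is a rounded judgement.

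Much of this stands, and it limits the weight of the point. The limiting words are indeed absent, and no planned analysis is affected. But the sentence is drawn as a conclusion from a test with a stated alpha and power, so a minimum is its natural reading. On the milder reading, the document still never says which observed result identifies efficacy. The descriptive reporting in Section 14 does not fill the gap: the exact 95% interval there is promised for sustained remission, which is not clearly the same quantity as relapse-free at week 52. The worry about lowering the bar bears on the choice of remedy, and it can be met by keeping 10 and stating its power.

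**Conclusion.** The concern holds. The power of 80% and the boundary of 10 cannot describe the same rule: with n = 15, a 30% null and one-sided 0.05, the stated power belongs to a boundary of 9 of 15. As a minimum, 10 of 15 has 62.9% power at the assumed 67%, a shortfall of about 17 points against the stated 80%.

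The conclusion rests on Section 13's own inputs and on reading its last sentence as a minimum. The sample size and the power statement are correct and need no change. The consequence is confined to interpretation of a secondary endpoint and can only understate a signal. It should be corrected because it is the sole efficacy benchmark and the correction is small; it is not a flaw in the design.

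**What to change.** Replace the last sentence of Section 13 in one of two ways.

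1. State the boundary. Suggested text: *Against a benchmark of 30%, the exact one-sided 0.05 binomial boundary is 9 or more of 15 (60%) subjects relapse-free at week 52 (attained alpha 1.5%; power 80.5% at a true rate of 67%). This is an interpretive benchmark; no formal test is planned.*
2. Keep 10 of 15 as a deliberately stricter minimum, and say that it has attained alpha 0.4%, 63% power at 67%, and 80% power only for a gain of about 43 points.

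The trial is open-label, so the amendment log should record that the change was made without reference to outcome data. If that cannot be said truthfully, the second option is safer because it does not lower the bar. Under either option the 30% benchmark should stand beside the cut-off, because the error depends on it; this matters more for 9 than for 10.

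The cost is one sentence and one log entry. Section 14 can remain descriptive. Optionally, it could add the exact 95% interval for the proportion relapse-free at week 52 beside the planned Kaplan-Meier estimate.
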